## **STATISTICAL PRINCIPLES**

### **Level of confidence intervals and p-values**

For this noninferiority trial, the upper bound of the 2-sided 95% confidence interval for the treatment effect has to be below the margin to declare that noninferiority has been shown. P-values <0.05 will be considered statistically significant.

### Adherence and protocol deviations

All substantial protocol violations will be listed. Adherence to study treatment (Table 1) will be defined as having consumed 100% of the study medicine, measured by self-report in the medication diary. This will be supported by the participant's returned medication weight/volume.

Table 1: Adherence to study treatment

	Standard treatment (n = xxx)	Placebo (n = xxx)
Self-reported daily dose (mg/m  /day)		
Week 1		
Week 2		
Week 3		
Week 4		
Participants returning study medication	n/N (%)	n/N (%)
Participants consuming 100% prescribed dose		
Medication diary	n/N (%)	n/N (%)
Returned medication count	n/N (%)	n/N (%)

### Analysis populations

The main analysis will consist of an intention-to-treat analysis. Participants who are lost to follow-up or in whom trial medication is stopped prematurely will be analyzed according to their allocated groups. In addition, as intention-to-treat analysis may increase the risk of type 1 errors in a non-inferiority trial, a per-protocol analysis will also be conducted.[5]

## STUDY POPULATION

### Screening data

Pediatric patients with steroid sensitive nephrotic syndrome are eligible for enrolment.

#### Eligibility

- Age over 1 and less than 18 years;
- Steroid sensitive nephrotic syndrome with at least 1 episode of nephrotic syndrome in the preceding 24 months.

This will include the following groups:

- Subjects without maintenance immunosuppressive therapy;
- Subjects with maintenance immunosuppressive therapy:
  - Long term immunosuppressive therapies: levamisole, ciclosporine, tacrolimus, mycophenolate mofetil (Cellcept®), mycophenolate sodium (Myfortic®), prednisolone max. 4 mg/m^2 on alternate days
  - Cyclophosphamide (oral or intravenous), at least three months post completion of therapy
  - A single dose or course of intravenous rituximab, at least three months post completion of therapy
- The last prednisolone use (at a dose over 10 mg/m^2 on alternate days) for the treatment of a previous episode was at least 4 weeks ago.

- Subjects experience a relapse nephrotic syndrome, defined as Albustix positive proteinuria (3+ or higher) for three consecutive days or the presence of generalized edema plus 3+ proteinuria on a single occasion.

#### Exclusion criteria

[figure not shown]
A potential subject who meets any of the following criteria will be excluded from participation in this study:

- Steroid resistant nephrotic syndrome;
- Receiving, or within 3 months after receiving, cyclophosphamide or rituximab;
- Daily prednisolone maintenance therapy at any dose;
- Alternate day prednisolone maintenance therapy at a dose over 4 mg/m^2;
- Documented or suspected significant non-compliance;
- Pregnancy;
- Stimulant drug use;
- Comorbidity:
  - Kidney transplant recipient
  - Any disease that requires the variation in oral prednisolone to be at the discretion of the treating physician(s)
- Concomitant use of moderate and strong CYP3A inducers;
- Concomitant use of moderate and strong CYP3A inhibitors, other than cyclosporine.

#### Recruitment

Subjects will be notified via their treating physician, via the patient association and/or the study website about the existence of the RESTERN study. Subjects will be recruited by the research team at the Radboudumc. The trial profile and inclusion will be shown in a Consolidated Standards of Reporting Trials (CONSORT) flow diagram (Figure 1), including the total number of randomised patients and per treatment group the numbers receiving allocated treatment, withdrawing consent, and lost to follow up.

Figure 1: CONSORT flow diagram

### Withdrawal/follow-up

Patients randomised who did not take their allocated treatment will be considered as having deviated from the protocol. Their data will be included in both the intention-to-treat and per-protocol analyses. If a patient or their representative withdraws consent for data collection, only data up to the point of withdrawal will be used in the analysis.

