## **STUDY METHODS**

### **Trial design**

National, single center, double-blind, randomised, placebo controlled, noninferiority intervention study.

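### The per-protocol analysis keeps patients who did not take their allocated treatment, so it gives no protection against dilution from them

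*SAP*

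**What the plan says.** The trial is described under Trial design as a "National, single center, double-blind, randomised, placebo controlled, noninferiority intervention study".

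Under Analysis populations, "The main analysis will consist of an intention-to-treat analysis". The same section gives the reason for a second analysis: "as intention-to-treat analysis may increase the risk of type 1 errors in a non-inferiority trial, a per-protocol analysis will also be conducted".

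Under Withdrawal/follow-up, "Patients randomised who did not take their allocated treatment will be considered as having deviated from the protocol". The next sentence reads: "Their data will be included in both the intention-to-treat and per-protocol analyses".

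Under Adherence and protocol deviations, adherence "will be defined as having consumed 100% of the study medicine, measured by self-report in the medication diary", and "All substantial protocol violations will be listed". Neither the adherence definition nor the list of violations is used to define the per-protocol set. The SAP states no criterion for leaving a patient out of that set.

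**The concern.** A per-protocol analysis accompanies intention-to-treat in a noninferiority trial because patients who do not follow their allocation tend to make the arms look alike, and likeness is what the trial sets out to show. The SAP gives this reason itself and then keeps in the per-protocol set the patients who most plainly did not follow their allocation.

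The direction of the bias can be read from the design. Under Randomisation, both arms have two weeks of alternate-day prednisolone and then differ by four weeks of prednisolone or placebo. Under Primary outcome, the placebo group's last prednisolone dose falls at the start of study medication. A standard-arm child who takes none of it therefore has about the same prednisolone exposure as a reduced-arm child. Skipping placebo changes no active exposure, so the other arm produces no offsetting effect.

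At stake is a noninferiority claim that is too easy to reach because of non-takers, with a supporting analysis that cannot reveal it.

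**Working it through.** **Inputs from the SAP.** SD 120 days, margin 50 days, 72 per group, power 80% (Sample size); allocation 1:1 (Randomisation); two-sided 95% confidence interval, that is one-sided 0.025 (Level of confidence intervals and p-values).

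**Assumed input.** The share f of the standard arm that takes no study medication. The SAP gives no figure, so 5%, 10% and 20% are shown.

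**The plan's own figure.** With true difference 0, n per group = 2 × (z for alpha + z for power)² × 120² / 50².
- One-sided 0.05: 2 × (1.6449 + 0.8416)² × 5.76 = 71.2, so 72. This reproduces the SAP.
- One-sided 0.025: 2 × (1.9600 + 0.8416)² × 5.76 = 90.4, so 91. With 72 per group the power is Φ(50/20 − 1.96) = 70.5%.

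The mismatch in alpha is a separate matter and does not affect this point. The analysis level of one-sided 0.025 is used below.

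**Standard error.** 120 × √(2/72) = 20 days.

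**Dilution.** Suppose the true loss among takers equals the margin, 50 days, and non-takers in the standard arm behave like the reduced arm. The observed difference is then 50(1 − f), and the probability of wrongly declaring noninferiority is Φ((50 − 50(1 − f))/20 − 1.96) = Φ(2.5f − 1.96).

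| f | Observed difference (days) | False noninferiority rate |
|---|---|---|
| 0 | 50 | 2.5% |
| 5% | 47.5 | Φ(−1.835) = 3.3% |
| 10% | 45 | Φ(−1.71) = 4.4% |
| 20% | 40 | Φ(−1.46) = 7.2% |

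Because non-takers are in both sets as written, the inflation from them is the same in the intention-to-treat and per-protocol analyses. If they are excluded, and exclusion introduces no selection bias, the per-protocol rate returns to 2.5%.

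**Price of exclusion.** If a share of each arm is excluded from 72 randomised per group and the true difference is 0, power is Φ(50/(120 × √(2/n)) − 1.96):
- none excluded, n = 72: 70.5%
- 5% excluded, n = 68.4: 68.3%
- 10% excluded, n = 64.8: 66.0%
- 20% excluded, n = 57.6: 60.9%

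**The case against.** **Reach.** A reader might infer that the per-protocol analysis merely repeats intention-to-treat and is worthless as a safeguard. The SAP does not support that. The sentence concerns only patients who did not take their allocated treatment. It does not say that part takers, ineligible patients or other violators stay in the per-protocol set, and the protocol, which is not shown, may hold further rules. This objection stands, so the point is limited to non-takers. A protocol definition could not cancel the explicit SAP sentence; a different rule there would add a second conflict.

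**Size.** The share f has no source, and the exclusion criteria already bar known or suspected significant non-compliance, so 20% is an extreme case. At 5% (about 4 of 72 children) the rise is 0.8 percentage points. The calculation tests a mean difference, whereas the SAP's default for the primary endpoint is a Mann-Whitney test with a log-rank comparison. It also assumes that a non-taker contributes the reduced-schedule mean, although the standard-arm clock starts at the end of study medication and the SAP does not say how it runs for a child who took none. All of this stands: the figures are illustrative, and the true effect could be smaller or larger.

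**Importance.** The sentence does not alter the main analysis, and the blind review before unblinding already allows final amendments to the SAP. Both are true. They make the correction easy but do not remove the contradiction in the only safeguard the SAP names against this bias.

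**Remedy.** Excluding patients by adherence can itself bias the comparison. If the 100% consumption standard defined the set, a child who relapsed during the study-medication weeks and therefore stopped could be dropped. If the reduced schedule led to more early relapses, this would remove them selectively from the placebo arm and favour noninferiority. This stands and shapes the fix.

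**Conclusion.** The SAP is wrong as written on this point. Its rule for non-takers contradicts the purpose it gives the per-protocol analysis, and no other section repairs it. The per-protocol analysis gives no protection against dilution from patients who did not take their allocated treatment, and that dilution acts towards noninferiority.

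The size depends on how many such patients there are, which the SAP does not say. The inflation shown above, from under one percentage point to almost five, rests on an assumed share in the standard arm, a normal-theory interval for a mean difference, a true loss equal to the margin, and non-takers who behave like the reduced arm. It is not an estimate of the error rate of the planned tests.

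A reader might also infer that noninferiority may be claimed only if both analyses support it. The SAP says only that the per-protocol analysis is done in addition, so the lack of such a rule is not an error.

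**What to change.** Replace the sentence under Withdrawal/follow-up with wording such as: *These patients are included in the intention-to-treat analysis and excluded from the per-protocol analysis.*

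Fix the list of per-protocol exclusions at the blind review described under Blinding, before unblinding. The list should say whether patients who took only part of their study medication are excluded, since the SAP has a 100% consumption standard but does not link it to this set. It should also state that a patient who stopped study medication because of a relapse is not excluded for that reason, because the relapse is the outcome.

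The change needs a few sentences of SAP text and no new data. It costs a smaller per-protocol set and a wider confidence interval: in the calculation above, power falls from 70.5% to 66.0% at one-sided 0.025 if 10% of each arm is excluded. Requiring both analyses to support noninferiority is an option for the sponsor and not part of this correction.

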### Baseline patient characteristics

Discrete variables will be demonstrated by frequencies and percentages. Continuously distributed variables will be demonstrated using either mean  $\pm$  standard deviation for data with normal distribution, or median and interquartile range for non-normally distributed data.

Table 2: Participant baseline characteristics

	Standard treatment (n = xxx)	Placebo (n = xxx)
Participant characteristics		
Male, n (%)	n/N (%)	n/N (%)
Age, years; median (IQR)	xx.x (xx.x to xx.x), n	xx.x (xx.x to xx.x), n
Age at onset, years; median (IQR)	xx.x (xx.x to xx.x), n	xx.x (xx.x to xx.x), n
Descent, n (%)	n/N (%)	n/N (%)

- Caucasian - Asian - African - Other, specify		
Maintenance therapy, n (%) - Levamisole - Cyclosporine - Tacrolimus - Mycophenolate mofetil - Mycophenolate sodium - Prednisolone	n/N (%)	n/N (%)
Total number of relapses prior to study participation	n/N (%)	n/N (%)
Number of relapses in preceding 24 months	n/N (%)	n/N (%)

## ANALYSIS

### Outcome definitions

#### Primary outcome

##### Time to first relapse

- Definition: time to first relapse (=first day of treatment of the next relapse) after the final prednisolone dose. The final prednisolone dose represents the beginning of study medication for the placebo group and the end of study medication for the prednisolone group.
- Timing: censored at 12 and 24 months
- Measurement value: days

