### **Sample size**

From previous studies, we know the incidence of nephrotic syndrome in Dutch children to be 1.52/100,000 children/year.[2] Eighty percent of the pediatric patients develop at least 1 relapse of whom 50% continue towards frequent relapsing nephrotic syndrome. Based on data from previous studies, average time to relapse in the first year is approximately 185 days (standard deviation of 120 days).[3] Using the power calculation for a noninferiority trial with a continuous primary outcome, a power of 80% and a noninferiority limit of 50 days, 72 patients per group are required. Using a Cox Proportional Hazard time-to-relapse analysis (survival analysis)[4], similar numbers can be calculated.

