### **Timing of final analysis**

Final analysis will take place after completion of the 24 months follow-up period of the last study subject.

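### The primary outcome has two censoring horizons (12 and 24 months) but one 50-day noninferiority limit, and the plan does not say which horizon decides

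*SAP*

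**What the plan says.** - **Outcome definitions, Time to first relapse:** the primary outcome carries "Timing: censored at 12 and 24 months" and "Measurement value: days". Neither horizon is given priority.
- **Sample size:** the design inputs are "average time to relapse in the first year is approximately 185 days (standard deviation of 120 days") and "a power of 80% and a noninferiority limit of 50 days, 72 patients per group are required". The method is described as "Using the power calculation for a noninferiority trial with a continuous primary outcome", which is a comparison of mean days.
- **Level of confidence intervals and p-values:** noninferiority requires that "the upper bound of the 2-sided 95% confidence interval for the treatment effect has to be below the margin". Neither the horizon nor the effect measure is named.
- **Timing of final analysis:** "Final analysis will take place after completion of the 24 months follow-up period of the last study subject". Both readings will therefore be available when the verdict is drawn.
- **Analysis methods, Primary endpoint:** the list includes a Mann-Whitney comparison of medians, person-time rates where patients have no relapse or are lost, a t test if the data look normal, percentages relapsed at 12 and at 24 months, and Kaplan-Meier with log-rank. None of these is linked to the 50 days.

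The SAP gives no separate 24-month limit and no rule for the case where the two horizons disagree.

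**The concern.** For an effect measured in mean days, the horizon is part of the definition of the effect. Relapse-free time counted up to 24 months has a longer mean and a wider spread than the same quantity counted up to 12 months. A given relative worsening therefore costs more days, and the estimate is less precise. A limit of 50 days chosen beside a one-year mean and SD becomes a different and harder standard when read at two years.

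Because the plan does not choose, a report could rest the noninferiority claim on either horizon. The Blinding section says that the final analyses can only be done after unblinding. A horizon chosen at that stage could be chosen with the results in view.

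**Working it through.** **1. The plan's own figure.** For a noninferiority comparison of means, n per group = 2(z_alpha + z_beta)² SD² / margin².
- One-sided 0.05: 2 × (1.645 + 0.842)² × 120² / 50² = 71.2, so 72. This matches the plan.
- One-sided 0.025, which is what the 2-sided 95% interval implies: 90.4, so 91. At 72 per group the power is then 70.5%.

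The match confirms that the 50 days was used as a difference in mean days. The mismatch in alpha is a separate matter. It lowers the pass rates at both horizons below but does not cause the gap between them.

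**2. Assumptions for comparing horizons.** Constant relapse hazard λ per day, no dropout, 72 per group, and relapse-free time counted up to T = 365 or 730 days. The documents do not fix λ, so three calibrations are used:
- A: mean up to 12 months equal to 185 days (Sample size), λ = 0.00427.
- B: 30% relapsed at 5.5 months (Interim analysis), λ = −ln(0.7)/(5.5 × 30.44) = 0.00213.
- C: mean without truncation equal to 185 days, λ = 1/185 = 0.00541.

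**3. Formulas.**
- Restricted mean M(T) = (1 − e^(−λT))/λ.
- Variance = (2/λ²)[1 − e^(−λT)(1 + λT)] − M(T)².
- Implied hazard ratio: the h for which M falls by 50 days when λ becomes hλ.
- SE of the difference = SD × √(2/72) = SD/6.
- Pass rate with equal arms = Φ(50/SE − 1.96).

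Example, A: at 12 months SE = 128/6 = 21.4 and Φ(2.34 − 1.96) = 65%. At 24 months SE = 199/6 = 33.2 and Φ(1.51 − 1.96) = 33%.

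**4. Results (12 months v 24 months).**

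| | A | B | C |
|---|---|---|---|
| Mean, days | 185 v 224 | 254 v 370 | 159 v 181 |
| SD, days | 128 v 199 | 128 v 257 | 122 v 170 |
| 50 days as share of mean | 27% v 22% | 20% v 14% | 31% v 28% |
| Hazard ratio equal to 50 days | 1.59 v 1.33 | 1.68 v 1.26 | 1.62 v 1.40 |
| Days lost at hazard ratio 1.5 | 44 v 69 | 38 v 88 | 42 v 58 |
| Pass rate, equal arms | 65% v 33% | 65% v 21% | 69% v 42% |

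A hazard ratio of 1.5 is what one third earlier (Interim analysis) means under a constant hazard. Its true loss lies inside 50 days at 12 months and outside at 24 months in all three calibrations.

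**5. How often the two readings differ.** Simulation of 20,000 trials, with noninferiority shown if the upper 95% limit of standard minus reduced is below 50 days:
- true hazard ratio 1.0: A 31%, B 44%, C 26%
- true hazard ratio 1.2: A 22%, B 29%, C 21%
- true hazard ratio 1.5: A 4%, B 7%, C 5%

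Nearly all differences are noninferiority shown at 12 months and not shown at 24.

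**6. What a 24-month decision would need on this scale.** Carrying the 12-month hazard ratio to 24 months gives a limit of about 68 to 111 days. Keeping 50 days at 24 months needs 144 to 326 per group at one-sided 0.05, or 183 to 414 at one-sided 0.025.

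**The case against.** The strongest reply is that mean days is not the scale of the listed analyses. The SAP puts a Mann-Whitney comparison of medians first and moves to person-time rates when patients remain relapse-free. Under calibration B, about 46% would be relapse-free at 12 months and 21% at 24, so that move would be triggered. Under proportional hazards a rate ratio sets the same standard at both horizons. With an assumed limit of 185/135 = 1.37, the readings differ in 12 to 20% of trials with equal arms, from precision alone. In B, 24 months is then the more powerful horizon (about 39% v 28%). Control medians are 128 to 325 days in the three calibrations, all below 365, so the horizon leaves them unchanged; the simulated disagreement was 5 to 8%, which in A and C is resampling noise.

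This stands as a limit on the size of the problem, but it does not settle which horizon decides. A rate ratio cannot be compared with 50 days. Mann-Whitney compares ranks, and its matching shift estimate (Hodges-Lehmann) differed between horizons in 8 to 58% of trials with equal arms. The only calculation in the SAP that uses the 50 days is on means.

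A reader might infer three stronger things that the SAP does not support:
- **That the plan orders a 50-day test at each horizon.** It speaks of one margin and one treatment effect and leaves the horizon open.
- **That the horizons give opposite conclusions.** The difference is between shown and not shown, not between noninferior and inferior, and it becomes uncommon once the reduced schedule is clearly worse.
- **That noninferiority is out of reach at 24 months whatever the method.** That depends on the scale, as the rate-ratio figures show.

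**Conclusion.** The gap is real and needs closing. One primary outcome has two horizons, one limit derived beside first-year data, and no statement of which horizon decides. On the mean-days scale used for the sample size, the 24-month reading is the stricter and noisier one in every calibration tried. The implied hazard ratio is about 1.3 to 1.4 rather than 1.6 to 1.7, and the equal-arm pass rate is 21 to 42% rather than 65 to 69%. The readings differ in about 26 to 44% of trials with equal arms and in 4 to 7% at a true hazard ratio of 1.5.

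The direction is firm on that scale. The sizes rest on a constant hazard, no dropout and 72 per group. They do not carry over to rate ratios or to medians below 12 months. Naming the horizon alone would not be enough, because the 50 days is also not attached to any listed effect measure.

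**What to change.** Amend the SAP before unblinding:
1. In the definition of time to first relapse, name 12 months as the single horizon for the noninferiority decision. This matches the first-year mean and SD in the sample size section.
2. In the confidence interval section and the primary endpoint analysis, state the one effect measure in days to which the 50-day limit applies, and its sign. One example is the difference in restricted mean relapse-free time to 12 months, standard minus reduced, with its 2-sided 95% confidence interval.
3. Report 24-month time to first relapse as supportive, with a confidence interval and without the 50-day test.
4. State the hazard ratio that 50 days implies at 12 months (1.59 to 1.68 in the calibrations above), so that it can be set against the one-third figure in the interim analysis section.

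The cost is SAP wording only. The downside is that relapses in year two no longer count toward the noninferiority decision, though they are still reported. If the sponsor prefers 24 months as decisive, the limit and the sample size need a justification at that horizon, because the present inputs do not supply one.

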#### Secondary outcomes

##### 1. Number of relapses

- Definition: number of relapses per patient after the final prednisolone dose
- Timing: censored at 12 and 24 months
- Measurement value: number of patients (%)

##### 2. Progression to frequent relapsing nephrotic syndrome

- Definition (according to KDIGO criteria): four or more relapses in any 12-month period
- Timing: censored at 24 months
- Measurement value: number of patients (%)

